5.2.2 Timing of Dose Administration

Trial treatment should be administered on Day 1 of each cycle after all procedures/assessments have been completed as detailed on the Trial Flow Chart (Section 6.0). Trial treatment may be administered up to 3 days before or after the scheduled Day 1 of each cycle due to administrative reasons.

All trial treatments will be administered on an outpatient basis. Patients will be monitored per individual site institutional standard of care policy during administration of ipilimumab and pembrolizumab.

Pembrolizumab 200 mg will be administered as a 30 minute IV infusion every 3 weeks. Sites should make every effort to target infusion timing to be as close to 30 minutes as possible. However, given the variability of infusion pumps from site to site, a window of -5 minutes and +10 minutes is permitted (i.e., infusion time is 30 minutes: -5 min/+10 min). Pembrolizumab should always be administered first when in combination with ipilimumab.

The Pharmacy Manual contains specific instructions for the preparation of the pembrolizumab infusion fluid and administration of infusion solution.

Ipilimumab will be administered once every 3 weeks for a total of 4 doses. Ipilimumab may be administered as either a 30 or 90 minute IV infusion. For additional instructions regarding dosing please refer to the ipilimumab label.

5.2.3 Trial Blinding/Masking

This is an open-label trial; therefore, the Sponsor, investigator and subject will know the treatment administered.

5.3 Randomization or Treatment Allocation

There is no randomization within the study however study participants will be allocated to a treatment arm based on prior progressive disease on anti-PD1/L1 antibody alone or PD1/L1 combination not including CTLA4 Ab.

5.4 Stratification

None

5.5 Concomitant Medications/Vaccinations (allowed & prohibited)

Medications or vaccinations specifically prohibited in the exclusion criteria are not allowed during the ongoing trial. If there is a clinical indication for one of these or other medications or vaccinations specifically prohibited during the trial, discontinuation from trial therapy or vaccination may be required. The investigator should discuss any questions regarding this with the Principal Investigator. The final decision on any supportive therapy or vaccination rests with the investigator and/or the subject's primary physician.

5.5.1 Acceptable Concomitant Medications

All treatments that the investigator considers necessary for a subject's welfare may be administered at the discretion of the investigator in keeping with the community standards of medical care. All concomitant medication will be recorded including all prescription, over-the-counter (OTC), herbal supplements, and IV medications and fluids. If changes occur during the trial period, documentation of drug dosage, frequency, route, and date may also be recorded.

5.5.2 Prohibited Concomitant Medications

Subjects are prohibited from receiving the following therapies during the Screening and Treatment Phase (including retreatment for post-complete response relapse) of this trial:

- Antineoplastic systemic chemotherapy or biological therapy
- Immunotherapy not specified in this protocol
- Chemotherapy
- Investigational agents other than pembrolizumab and ipilimumab
- Radiation therapy
 - Note: Radiation therapy to a symptomatic solitary lesion or to the brain may be allowed after discussion between the investigator and Principal Investigator.
- Live vaccines within 30 days prior to the first dose of trial treatment and while participating in the trial. Examples of live vaccines include, but are not limited to, the following: measles, mumps, rubella, varicella/zoster, yellow fever, rabies, BCG, and typhoid vaccine.
- Systemic glucocorticoids for any purpose other than to modulate symptoms from an
 event of clinical interest of suspected immunologic etiology. The use of physiologic
 doses of corticosteroids may be approved after consultation with the Principal
 Investigator.

Subjects who, in the assessment by the investigator, require the use of any of the aforementioned treatments for clinical management should be removed from the trial. Subjects may receive other medications that the investigator deems to be medically necessary.

Local surgery resulting from disease progression is prohibited. However, if indicated for palliative measure and after Principal Investigator approval, local surgery may be permitted after the Week 12 tumor assessment. Subjects who, in the assessment by the investigator, require the use of any of the aforementioned treatments for clinical management should be removed from the trial. Subjects may receive other medications that the investigator deems to be medically necessary.

The Exclusion Criteria describes other medications which are prohibited in this trial.

There are no prohibited therapies during the Post-Treatment Follow-up Phase.

5.6 Rescue Medications & Supportive Care

5.6.1 Supportive Care Guidelines

Subjects should receive appropriate supportive care measures as deemed necessary by the treating investigator. Suggested supportive care measures for the management of adverse events with potential immunologic etiology are outlined below. Where appropriate, these guidelines include the use of oral or intravenous treatment with corticosteroids as well as additional anti-inflammatory agents if symptoms do not improve with administration of corticosteroids. Note that several courses of steroid tapering may be necessary as symptoms may worsen when the steroid dose is decreased. For each disorder, attempts should be made to rule out other causes such as metastatic disease or bacterial or viral infection, which might require additional supportive care. The treatment guidelines are intended to be applied when the investigator determines the events to be related to pembrolizumab and/or ipilimumab.

It may be necessary to perform conditional procedures such as bronchoscopy, endoscopy, or skin photography as part of evaluation of the event.

• Pneumonitis:

- For Grade 2 events, treat with systemic corticosteroids. When symptoms improve to Grade 1 or less, steroid taper should be started and continued over no less than 4 weeks.
- For Grade 3-4 events, immediately treat with intravenous steroids.
 Administer additional anti-inflammatory measures, as needed.
- Add prophylactic antibiotics for opportunistic infections in the case of prolonged steroid administration.

Diarrhea/Colitis:

Subjects should be carefully monitored for signs and symptoms of enterocolitis (such as diarrhea, abdominal pain, blood or mucus in stool, with or without fever) and of bowel perforation (such as peritoneal signs and ileus).

- All subjects who experience diarrhea/colitis should be advised to drink liberal quantities of clear fluids. If sufficient oral fluid intake is not feasible, fluid and electrolytes should be substituted via IV infusion. For Grade 2 or higher diarrhea, consider GI consultation and endoscopy to confirm or rule out colitis.
- o For **Grade 2 diarrhea/colitis** consider early administration of oral corticosteroids, especially if symptoms persists greater than 3 days,.
- For Grade 3 or 4 diarrhea/colitis consider early administration of corticosteroids and if symptoms persist > 1 week, treat with intravenous steroids followed by high dose oral steroids.
- When symptoms improve to Grade 1 or less, steroid taper should be started and continued over no less than 4 weeks.

• Type 1 diabetes mellitus (if new onset, including diabetic ketoacidosis [DKA]) or ≥ Grade 3 Hyperglycemia, if associated with ketosis (ketonuria) or metabolic acidosis (DKA)

- o For **T1DM** or **Grade 3-4** Hyperglycemia
 - Insulin replacement therapy is recommended for Type I diabetes mellitus and for Grade 3-4 hyperglycemia associated with metabolic acidosis or ketonuria.
 - Evaluate patients with serum glucose and a metabolic panel, urine ketones, glycosylated hemoglobin, and C-peptide.

• Hypophysitis:

- o For **Grade 2** events, treat with corticosteroids. When symptoms improve to Grade 1 or less, steroid taper should be started and continued over no less than 4 weeks. Replacement of appropriate hormones may be required as the steroid dose is tapered.
- For **Grade 3-4** events, treat with an initial dose of IV corticosteroids followed by oral corticosteroids. When symptoms improve to Grade 1 or less, steroid taper should be started and continued over no less than 4 weeks. Replacement of appropriate hormones may be required as the steroid dose is tapered.

• Hyperthyroidism or Hypothyroidism:

Thyroid disorders can occur at any time during treatment. Monitor patients for changes in thyroid function (at the start of treatment, periodically during treatment, and as indicated based on clinical evaluation) and for clinical signs and symptoms of thyroid disorders.

- o **Grade 2** hyperthyroidism events (and **Grade 2-4** hypothyroidism):
 - In hyperthyroidism, non-selective beta-blockers (e.g. propranolol) are suggested as initial therapy.

• In hypothyroidism, thyroid hormone replacement therapy, with levothyroxine or liothyroinine, is indicated per standard of care.

o **Grade 3-4** hyperthyroidism

Treat with an initial dose of IV corticosteroid followed by oral corticosteroids. When symptoms improve to Grade 1 or less, steroid taper should be started and continued over no less than 4 weeks. Replacement of appropriate hormones may be required as the steroid dose is tapered.

• Hepatic:

- For **Grade 2** events, monitor liver function tests more frequently until returned to baseline values (consider weekly).
 - Treat with IV or oral corticosteroids
- o For **Grade 3-4** events, treat with intravenous corticosteroids for 24 to 48 hours.
- When symptoms improve to Grade 1 or less, a steroid taper should be started and continued over no less than 4 weeks.

• Renal Failure or Nephritis:

- o For Grade 2 events, treat with corticosteroids.
- o For **Grade 3-4** events, treat with systemic corticosteroids.
- o When symptoms improve to Grade 1 or less, steroid taper should be started and continued over no less than 4 weeks.
- Management of Infusion Reactions: Signs and symptoms usually develop during or shortly after drug infusion and generally resolve completely within 24 hours of completion of infusion.

Infusion reactions to ipilimumab will be managed by the investigators according to the product labels.

Table 4 below shows treatment guidelines for subjects who experience an infusion reaction associated with administration of pembrolizumab. Infusion reactions to ipilimumab will be managed by the investigators according to the product labels.

Table 4 Infusion Reaction Treatment Guidelines

NCI CTCAE Grade	Treatment	Premedication at subsequent dosing
Grade 1 Mild reaction; infusion interruption not indicated; intervention not indicated	Increase monitoring of vital signs as medically indicated until the subject is deemed medically stable in the opinion of the investigator.	None
Grade 2	Stop Infusion and monitor symptoms.	Subject may be premedicated 1.5h
Requires infusion interruption but	Additional appropriate medical therapy may	$(\pm 30 \text{ minutes})$ prior to infusion of
responds promptly to symptomatic	include but is not limited to:	pembrolizumab
treatment (e.g., antihistamines,	IV fluids	(PEMBROLIZUMAB) with:
NSAIDS, narcotics, IV fluids);	Antihistamines	
	NSAIDS	

NCI CTCAE Grade	Treatment	Premedication at subsequent dosing				
prophylactic medications indicated for <=24 hrs	Acetaminophen Narcotics Increase monitoring of vital signs as medically	Diphenhydramine 50 mg po (or equivalent dose of antihistamine).				
	indicated until the subject is deemed medically stable in the opinion of the investigator. If symptoms resolve within one hour of stopping drug infusion, the infusion may be restarted at 50% of the original infusion rate (e.g., from 100 mL/hr to 50 mL/hr). Otherwise dosing will be held until symptoms resolve and the subject should be premedicated for the next scheduled dose. Subjects who develop Grade 2 toxicity despite adequate premedication should be permanently discontinued from further trial treatment administration.	Acetaminophen 500-1000 mg po (or equivalent dose of antipyretic).				
Grades 3 or 4	Stop Infusion.	No subsequent dosing				
Grade 3: Prolonged (i.e., not rapidly responsive to symptomatic medication and/or brief interruption of infusion); recurrence of symptoms following initial improvement; hospitalization indicated for other clinical sequelae (e.g., renal impairment, pulmonary infiltrates)	Additional appropriate medical therapy may include but is not limited to: IV fluids Antihistamines NSAIDS Acetaminophen Narcotics Oxygen Pressors Corticosteroids Epinephrine					
Grade 4: Life-threatening; pressor or ventilatory support indicated	Increase monitoring of vital signs as medically indicated until the subject is deemed medically stable in the opinion of the investigator. Hospitalization may be indicated. Subject is permanently discontinued from further trial treatment administration.					
Appropriate resuscitation equipment should be available in the room and a physician readily available during the period of drug administration.						

• Management of Stevens-Johnson syndrome and Toxic Epidermal Necrolysis:

To date, approximately 11,000 patients in clinical trials and 27,000 patients in the post-marketing setting have been treated with KEYTRUDA®. One fatal case of SJS in a clinical trial and one fatal case of TEN in the post-marketing setting have been reported in patients treated with KEYTRUDA®. Including these cases, there have been 8 cases of SJS (6 in clinical trials, and 2 post-marketing) and 2 cases of TEN (both post-marketing) all of which were serious.

- o For signs or symptoms of SJS or TEN, withhold KEYTRUDA® and refer the patient for specialized care for assessment and treatment.
- o If SJS or TEN is confirmed, permanently discontinue KEYTRUDA®.

• Management of Immune-mediated myocarditis:

A total of 6 cases of myocarditis have been reported in patients treated with KEYTRUDA® in clinical trials or in an expanded access program. There were was 1 fatal case reported in a clinical trial.

o For suspected immune-mediated myocarditis, ensure adequate evaluation to exclude other etiologies, and administer corticosteroids as appropriate.

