5.2.1.2 Dose Modification

Adverse events (both non-serious and serious) associated with pembrolizumab and/or ipilimumab exposure may represent an immunologic etiology. These adverse events may occur shortly after the first dose or several months after the last dose of treatment. Pembrolizumab and ipilimumab must be withheld for drug-related toxicities and severe or life-

threatening AEs as per Table 3 below. See Section 5.6.1 for supportive care guidelines, including use of corticosteroids.

All Grade 3-5 adverse events considered possibly, probably or definitely related to study agent(s) must be discussed with the Principal Investigator. All treating clinicians involved in the protocol are welcomed to discuss complicated cases at any time with the Principal Investigator:

[name], PhD
University of Chicago Comprehensive Cancer Center
[contact]

Table 3 Dose Modification Guidelines for Drug-Related Adverse Events

Toxicity	Hold Treatment For Grade	Timing for Restarting Treatment	Discontinue Subject (Includes both drugs unless stated)			
Diarrhea/Colitis		Toxicity resolves to Grade 0-1.	Toxicity does not resolve within 12 weeks of last dose or inability to reduce corticosteroid to 10 mg or less of prednisone or equivalent per day within 12 weeks. For Grade 3 diarrhea/colitis, permanently discontinue ipilimumab			
	4	Permanently discontinue both pembrolizumab and ipilimumab	Permanently discontinue both pembrolizumab and ipilimumab			
AST, ALT, or	2	Toxicity resolves to Grade 0-1	Toxicity does not resolve within 12 weeks of last dose.			
Increased Bilirubin	3-4	Permanently discontinue (see exception below) ¹	Permanently discontinue both pembrolizumab and ipilimumab			
Type 1 diabetes mellitus (if new onset) or Hyperglycemia	T1DM or 3-4	Hold pembrolizumab for new onset Type 1 diabetes mellitus or Grade 3-4 hyperglycemia associated with evidence of beta cell failure.	Resume pembrolizumab when patients are clinically and metabolically stable. Permanently discontinue ipilimumab.			
Hypophysitis	2-3	Toxicity resolves to Grade 0-1	Toxicity does not resolve within 12 weeks of last dose or inability to reduce corticosteroid to 10 mg or less of prednisone or equivalent per day within 12 weeks.			
	4	Permanently discontinue both pembrolizumab and ipilimumab	Permanently discontinue both pembrolizumab and ipilimumab			

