Hyperthyroidism	3	Toxicity resolves to Grade 0-1	Toxicity does not resolve within 12 weeks of last dose or inability to reduce corticosteroid to 10 mg or less of prednisone or equivalent per day within 12 weeks.			
	4	Permanently discontinue both pembrolizumab and ipilimumab	Permanently discontinue both pembrolizumab and ipilimumab			
Hypothyroidism	2-4	Therapy with pembrolizumab can be continued while treatment for the thyroid disorder is instituted	Therapy with pembrolizumab and ipilimumab can be continued while treatment for the thyroid disorder is instituted.			
Infusion Reaction	3-4	Permanently discontinue both pembrolizumab and ipilimumab	Permanently discontinue both pembrolizumab and ipilimumab			
Pneumonitis	2	Toxicity resolves to Grade 0-1	Toxicity does not resolve within 12 weeks of last dose or inability to reduce corticosteroid to 10 mg or less of prednisone or equivalent per day within 12 weeks.			
	3-4	Permanently discontinue both pembrolizumab and ipilimumab	Permanently discontinue both pembrolizumab and ipilimumab			
Renal Failure or 2		Toxicity resolves to Grade 0-1	Toxicity does not resolve within 12 weeks of last dose or inability to reduce corticosteroid to 10 mg or less of prednisone or equivalent per day within 12 weeks.			
Nephritis	3-4	Permanently discontinue both pembrolizumab and ipilimumab	Permanently discontinue both pembrolizumab and ipilimumab			
All Other Drug- Related Toxicity ²	3 or Severe	Toxicity resolves to Grade 0-1	Toxicity does not resolve within 12 weeks of last dose or inability to reduce corticosteroid to 10 mg or less of prednisone or equivalent per day within 12 weeks.			
Aciaica Toxicity	4	Permanently discontinue both pembrolizumab and ipilimumab	Permanently discontinue both pembrolizumab and ipilimumab			

Note: Permanently discontinue for any severe or Grade 3 drug-related AE that recurs or any life-threatening event.

1 For patients with liver metastasis who begin treatment with Grade 2 AST or ALT, if AST or ALT increases by greater than or equal to 50% relative to baseline and lasts for at least 1 week then patients should be discontinued.

² Patients with intolerable or persistent Grade 2 drug-related AE may hold study medication at physician discretion. Permanently discontinue study drug for persistent Grade 2 adverse reactions for which treatment with study drug has been held, that do not recover to Grade 0-1 within 12 weeks of the last dose.

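### Table 3's diabetes/hyperglycemia row sets two different triggers, so a Grade 3 event without beta cell failure may either end ipilimumab permanently or let both drugs restart

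*Combined protocol and SAP*

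**What the plan says.** Section 5.2.1.2 sends dosing decisions to Table 3. The row for new-onset Type 1 diabetes or hyperglycemia has three active cells:

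- **Hold column:** Type 1 diabetes, or Grade 3-4, with no further condition.
- **Restart column:** "Hold pembrolizumab for new onset Type 1 diabetes mellitus or Grade 3-4 hyperglycemia associated with evidence of beta cell failure". This cell adds a condition and names one drug only.
- **Discontinuation column**, headed "Discontinue Subject (Includes both drugs unless stated", closing bracket omitted here: "Resume pembrolizumab when patients are clinically and metabolically stable. Permanently discontinue ipilimumab".

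Drug-related events that no named row covers go to the All Other Drug-Related Toxicity row. At Grade 3 its restart condition is "Toxicity resolves to Grade 0-1", with 12-week limits on resolution and on steroid reduction. At Grade 4 it stops both drugs permanently.

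Section 5.2.1.2 cites section 5.6.1 for a different purpose: "See Section 5.6.1 for supportive care guidelines, including use of corticosteroids". The 5.6.1 heading takes in Type 1 diabetes and Grade 3 or higher "Hyperglycemia, if associated with ketosis (ketonuria) or metabolic acidosis (DKA", closing bracket omitted here. The sub-bullet beneath it covers Type 1 diabetes or Grade 3-4 hyperglycemia without that condition. Two instructions follow: "Insulin replacement therapy is recommended for Type I diabetes mellitus and for Grade 3-4 hyperglycemia associated with metabolic acidosis or ketonuria", and "Evaluate patients with serum glucose and a metabolic panel, urine ketones, glycosylated hemoglobin, and C-peptide".

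**The concern.** One table row should have one trigger. Here the hold column is unconditional and the adjacent cell is conditional, and nothing says which of them decides whether the row applies. The discontinuation cell then attaches a permanent stop of ipilimumab to whichever trigger is meant.

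Ipilimumab is the drug added in this trial, and it is given for four doses only. Two sites, or one site on two occasions, could manage the same laboratory event differently and each cite Table 3. That is first a safety matter, because the rule for permanently stopping a study drug is ambiguous. It also makes exposure uneven in a single-arm trial whose primary endpoint is response to the combination.

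**Working it through.** The plan states no figure on this point, so the check is to trace events through the text.

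**Inputs.** The three cells of the diabetes/hyperglycemia row and the All Other row (Table 3); the supportive care text (5.6.1); four ipilimumab doses at three-week intervals (Table 2); the rule that the ipilimumab course must be completed within 16 weeks of the first dose (5.2.1.2); 70 patients (10.2).

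**Step 1. Trace drug-related hyperglycemia under each reading.** Unqualified means that the hold column sets the trigger. Qualified means that the beta cell failure cell sets it.

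| Event | Unqualified reading | Qualified reading | Conflict |
|---|---|---|---|
| Grade 3, no Type 1 diabetes, no beta cell failure | Row applies: ipilimumab stops permanently, pembrolizumab may resume | Row does not apply; All Other row: both drugs may restart at Grade 0-1 within the 12-week limits | On ipilimumab |
| Grade 4, no Type 1 diabetes, no beta cell failure | Row applies: ipilimumab stops permanently, pembrolizumab may resume | All Other row: both drugs stop permanently | On pembrolizumab |
| Type 1 diabetes, or Grade 3-4 with beta cell failure | Ipilimumab stops permanently, pembrolizumab may resume | Same | None |

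At Grade 4, the note under Table 3 on life-threatening events also bears on the result, since Table 6 describes Grade 4 as life threatening. That rule is separate from the question of the row's trigger.

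**Step 2. Add section 5.6.1.** Its hyperglycemia text contains no instruction to hold, restart or stop a study drug. Changing its qualifier changes who is advised to receive insulin and, depending on how the heading is read, who gets the work-up. No cell in the table above changes. It is a third wording for a related event, not a third dosing rule.

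**Step 3. Size for one patient.** After dose 1, 4 − 1 = 3 ipilimumab doses remain; after dose 4, none remain and the ipilimumab conflict has no practical effect. The fourth dose falls 3 × 3 = 9 weeks after the first, so the 16-week rule leaves 16 − 9 = 7 weeks of slack. If the event takes longer than that to settle, ipilimumab ends under either reading.

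**Step 4. Size for the trial.** The documents give no incidence. If 1% to 5% of patients had any Grade 3-4 hyperglycemia (an assumption), that would be 70 × 0.01 = 0.7 to 70 × 0.05 = 3.5 patients. This is a ceiling, not the number affected. For the ipilimumab conflict the event must also be drug-related, Grade 3, free of Type 1 diabetes and beta cell failure, and before the fourth dose.

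**The case against.** **The row can be read coherently.** It places a hold instruction under the restart heading and a resume instruction under the discontinuation heading. That suggests one sentence running across the cells, with the hold column as a short label for it. On that view, events without beta cell failure simply belong to the All Other row. The reading is plausible, but the documents nowhere state it, and the plain meaning of a column that lists the grades at which treatment is held points the other way.

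**There is central oversight.** Section 5.2.1.2 requires every related Grade 3-5 event to be discussed with the Principal Investigator, and Principal Investigator approval is needed to continue pembrolizumab after ipilimumab is stopped for toxicity. Both apply here and reduce variation between sites. They do not resolve the conflict, because the Principal Investigator works from the same text.

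**Three stronger readings are tempting and do not stand.**

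- A reader might infer that both drugs can restart after any Grade 3-4 event. At Grade 4 the All Other row stops both.
- A reader might infer that the ketosis or acidosis condition in 5.6.1 decides dosing. That section is supportive care, and 5.2.1.2 cites it only as such.
- A reader might infer that beta cell failure without ketosis would go undetected, because C-peptide appears only under the restricted 5.6.1 heading, is absent from Table 5, and urinalysis is scheduled only at screening. The documents do not establish this. The work-up line sits under a sub-bullet covering all Grade 3-4 events and, unlike the insulin line, carries no qualifier of its own. It also orders urine ketones, so ketosis need not already be known. Glucose and bicarbonate are in the chemistry panel drawn each cycle, and sections 5.6.1 and 8.1 allow conditional and unscheduled procedures. What remains is that heading and sub-bullet disagree.

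**Conclusion.** The contradiction is real and lies within one Table 3 row. For drug-related Grade 3 hyperglycemia without Type 1 diabetes or beta cell failure, one reading ends ipilimumab permanently and the other allows both drugs to restart. At Grade 4 in the same patients, the readings differ on whether pembrolizumab may resume. The 5.6.1 wording is a secondary mismatch with no dosing effect of its own.

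For a single patient the consequence is up to 3 of 4 ipilimumab doses. Across the trial it probably concerns very few patients; the count cannot be given, because the documents report no incidence and the affected subset is only part of all Grade 3-4 hyperglycemia. The response-rate denominator is untouched, since section 10.1 counts any eligible patient who has received one dose of the combination. The conclusion assumes that an event not meeting the row's trigger passes to the All Other row, which is the table's only catch-all. The point merits correction as a safety inconsistency that is cheap to remove, not as a threat to the primary analysis.

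**What to change.** Reconcile the cells of the Table 3 diabetes/hyperglycemia row so that one stated trigger governs the hold, the resumption of pembrolizumab and the permanent stop of ipilimumab. State which row applies when that trigger is not met, at Grade 3 and at Grade 4. Align the 5.6.1 heading and sub-bullet so that the listed work-up clearly applies to the patients in whom Table 3 needs its result. The choice of trigger belongs to the sponsor, and no view on it is offered here.

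The cost is a wording change to one table row and one supportive care bullet. The small downside is that the listed laboratory work-up may be ordered in a few more patients.

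### For confirmed SJS/TEN, Section 5.6.1 stops only pembrolizumab, so ipilimumab falls to Table 3's catch-all row, which allows a conditional restart after a first Grade 3 event; myocarditis has a similar, weaker gap

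*Combined protocol and SAP*

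**What the plan says.** Section 5.6.1 applies to events judged related to either study drug. For suspected SJS/TEN it says: "For signs or symptoms of SJS or TEN, withhold KEYTRUDA® and refer the patient for specialized care for assessment and treatment". For confirmed disease: "If SJS or TEN is confirmed, permanently discontinue KEYTRUDA". For myocarditis it says only: "For suspected immune-mediated myocarditis, ensure adequate evaluation to exclude other etiologies, and administer corticosteroids as appropriate". That line contains no hold, restart or stop instruction for either drug.

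Table 3 in Section 5.2.1.2 has event-specific rows, none of them for SJS/TEN or myocarditis, and a final catch-all row for all other drug-related toxicity. In the catch-all row, a Grade 3 or severe event means hold, then restart at Grade 0-1. Discontinuation follows under this condition: "Toxicity does not resolve within 12 weeks of last dose or inability to reduce corticosteroid to 10 mg or less of prednisone or equivalent". The steroid limit is a daily dose and carries the same 12-week deadline. Grade 4 stops both drugs. A note adds: "Permanently discontinue for any severe or Grade 3 drug-related AE that recurs or any life-threatening event". At Grade 2, footnote 2 says: "Patients with intolerable or persistent Grade 2 drug-related AE may hold study medication at physician discretion". It then requires a permanent stop if a held, persistent Grade 2 event has not recovered within 12 weeks of the last dose.

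For Grade 3-4 pneumonitis, nephritis and infusion reactions, Table 3 is firm: "Permanently discontinue both pembrolizumab and ipilimumab".

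**The concern.** In this protocol it matters which drug a rule names. The discontinuation column of Table 3 covers both drugs by default and says so when it departs from that: Grade 3 colitis permanently stops ipilimumab only, and pembrolizumab may resume after new-onset type 1 diabetes. A site that reads an instruction to stop KEYTRUDA would reasonably take it to mean pembrolizumab. What happens to ipilimumab then depends on a general-purpose row that was not written for a severe skin reaction.

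Section 5.6.1 itself reports one fatal SJS case, one fatal TEN case and one fatal myocarditis case on pembrolizumab, and describes all ten SJS/TEN cases (8 + 2) as serious. This trial adds a second checkpoint antibody for four cycles. At stake is whether a patient who has recovered from one of these events could be re-exposed under a literal reading of the dose rules. The accuracy of the efficacy result is not at stake.

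**Working it through.** The plan states no figure on this point, so the check is mainly a comparison of its rules, followed by two short calculations.

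**1. What the written rules give for a first Grade 3, non-life-threatening event**

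| Event | Pembrolizumab | Ipilimumab | Source |
|---|---|---|---|
| SJS/TEN, confirmed | Permanent stop | Hold, conditional restart | 5.6.1; Table 3 catch-all row |
| Myocarditis | Hold, conditional restart | Hold, conditional restart | Table 3 catch-all row |
| Pneumonitis, nephritis, infusion reaction | Permanent stop | Permanent stop | Table 3 |
| Diarrhea/colitis | Hold, conditional restart | Permanent stop | Table 3 |
| Hypophysitis, hyperthyroidism | Hold, conditional restart | Hold, conditional restart | Table 3 |

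Grade 4, life-threatening and recurrent Grade 3 events stop both drugs whatever the event. The gap is therefore confined to a first event that is severe but not life-threatening.

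**2. Do the other rules close the gap?**

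- Section 5.2.1.2: "All Grade 3-5 adverse events considered possibly, probably or definitely related to study agent(s) must be discussed with the Principal Investigator". This is mandatory but prescribes no outcome.
- Section 8.2.3.1 has serious events reported to the Principal Investigator within 24 hours, and Section 12.4 provides weekly safety review. Neither sets a stopping rule for a drug.
- Table 6 in Section 8.2.4 requires advance approval for rechallenge with the Merck product after a serious, possibly related event. Table 7 lists only pembrolizumab as Merck-supplied. The rule therefore covers pembrolizumab after serious myocarditis, as an approval step, and does not reach ipilimumab.
- Section 5.8 lets the investigator withdraw a subject for any untoward effect. This is discretionary.

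**3. Does the 16-week ipilimumab limit (Section 5.2.1.2) block a restart?**

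- Doses are due at weeks 0, 3, 6 and 9, so the slack is 16 - 9 = 7 weeks.
- Latest restart that still completes four doses: after dose 1, week 16 - 6 = 10; after dose 2, week 16 - 3 = 13; after dose 3, week 16.
- The gap since the last dose is 10 weeks in each case (10 - 0, 13 - 3, 16 - 6). Since 10 < 12, the catch-all row's 12-week limit is not the binding one for a full course.
- Review by the Principal Investigator is required before resuming after more than 2 interrupted doses. Counting ipilimumab doses after dose 1, restart at week 9 misses weeks 3 and 6 (2 doses, no review), and restart at week 10 misses weeks 3, 6 and 9 (3 doses, review). This adds little, because the Principal Investigator must already have discussed the Grade 3 event.

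The limit narrows the window for a restart but does not close it.

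**4. Expected number of cases**

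- Inputs from 5.6.1: 6 SJS cases in about 11,000 clinical-trial patients; both TEN cases were post-marketing. Planned sample size: 70.
- 6/11,000 = 0.0545%, and 70 x 6/11,000 = 0.038.
- Exact Poisson 95% limits for 6 events are 2.20 and 13.06, giving 70 x 2.20/11,000 = 0.014 and 70 x 13.06/11,000 = 0.083.
- Timing is not given, so it is an assumption. If onset were spread evenly over 24 months, 9 of 104 weeks precede the fourth dose: 0.038 x 9/104 = 0.0033. If all onset were early, the figure stays at 0.038.
- Myocarditis: 6 cases from trials or an expanded access program, with no matching denominator. The 27,000 patients quoted for SJS/TEN are post-marketing patients and do not belong under that count, so no rate is calculated.

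**The case against.** The best case against is that a restart is very unlikely in practice. The Principal Investigator hears of every related Grade 3-5 event, with no minimum number of missed doses. A patient at Grade 0-1 who cannot taper steroids must stop. After SJS/TEN, restarting ipilimumab would also mean giving it alone, which the protocol nowhere describes: Section 5.8 has both drugs together and then pembrolizumab alone, and Section 5.2.1.2 provides only for continuing pembrolizumab after ipilimumab is stopped. All of this stands. It shows that the restart is improbable and awkward, not that it is barred.

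A reader might therefore infer that the catch-all row is the only written rule, or that the protocol directs sites to resume ipilimumab. The documents support neither. The row is the only grade-based hold/restart rule, and it operates alongside the safeguards above.

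Two sources are not available. Whether SJS, TEN or myocarditis can be graded 3 without being life-threatening depends on event-specific CTCAE v4.0 criteria; the protocol reproduces only the general definition, in Table 6. Section 5.2.2 refers to the ipilimumab label for further dosing instructions, and the label may settle the matter. However, where the protocol delegates toxicity management to a label, as for ipilimumab infusion reactions in 5.6.1, it says so, and it does not do so here.

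On myocarditis the objection has more force. Table 3's Grade 3 rules differ by event, and nothing in the documents shows which pattern myocarditis should follow.

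**Conclusion.** The SJS/TEN point holds. In a two-drug regimen the stop names one drug, and the remaining grade-based rule allows ipilimumab to restart, under conditions, after a first Grade 3, non-life-threatening event. Myocarditis is a secondary point: it is an omission rather than a conflict, and the case for a Grade 3 stop rests on a chosen comparison with pneumonitis.

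The size is very small: about 0.04 SJS cases in 70 patients (0.014 to 0.083), or 0.003 to 0.04 before the fourth dose depending on the timing assumption. A reader might take 0.04 as a ceiling. It is not one, because it applies a pembrolizumab rate to a combination for which the documents give no rate. The primary endpoint, the two-stage design and the sample size are unaffected. This is a low-priority, inexpensive safety clarification, and it assumes that such an event can be graded 3 and that the ipilimumab label does not already govern it.

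**What to change.** - In the two SJS/TEN action lines of Section 5.6.1, replace KEYTRUDA with pembrolizumab and ipilimumab.
- Add an SJS/TEN row to Table 3: withhold both drugs on suspicion; permanently discontinue both on confirmation.
- Add a myocarditis row to Table 3, modelled on the pneumonitis row: withhold both drugs on suspicion; at Grade 2 restart only at Grade 0-1 under the existing 12-week and prednisone conditions; permanently discontinue both at Grade 3-4. If the investigators prefer a different Grade 3 rule, they should state it.
- Refer to the new rows from the SJS/TEN and myocarditis paragraphs of 5.6.1.

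The cost is one wording amendment, with no added visits, tests or patients. A very few patients who recover would lose the option of re-treatment.
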